10.1.1 Analysis of Efficacy Endpoints by Variable Type

Time to events (TTE) variables

All TTE endpoints defined in this study are concerned with only the first incidence of an event of interest, and recurrence of the same event is not considered for endpoint derivation. An event however may be defined in a composite manner, i.e., as the occurrence of one among several different outcomes. The composite event is observed when at least one of the component events occurs, and the time to the earliest among the occurring component events is considered to be the TTE for the composite event.

Follow-up time for TTE endpoints will be derived as follows:

Date of first occurrence of an event or censoring – date of randomization + 1.

TTE endpoints will be computed in days and converted into months (1 month = 30.4375 days) for analysis. Thus, for subjects who experience the event of interest, time to event will be defined as the time from randomization to the first occurrence of the event. When multiple assessments are needed to ascertain the occurrence of an event, the earliest date among all of these assessments is taken to be date of the event or censoring. For a subject who does not experience an event on the study, time will be right censored at the time of his last available adequate post-baseline assessment that rules out the occurrence of the event. If a subject had no post-baseline assessment and did not experience the event of interest, then TTE will be censored at the date of randomization and we will set TTE = 1 day, by convention.

TTE endpoints will be summarized by number of events observed, number of subjects censored, and times corresponding to 25% (1st quartile), 50% (median) and 75% (3rd quartile) event probabilities. Kaplan-Meier (KM) estimates¹⁵ will be calculated and plotted. Comparison between treatment arms will be based on stratified weighted log-rank tests (only for OS) or stratified log-rank tests (for other TTE endpoints) as specified. Measure of treatment effects will be provided in term of HR (Depatux-M + RT/TMZ to Placebo + RT/TMZ) from Cox proportional hazards regression model adjusting for the main effects of the stratification factors with HR value less than 1 representing treatment benefit.

Deterioration Free Survival (DFS) variables for PRO assessments

All the DFS endpoints defined in this study are concerned with only the first incidence of a deterioration, and recurrence of the same event is not considered for endpoint derivation. The deterioration is defined as satisfying the deterioration criteria without further improvement (i.e., failing to satisfy deterioration criteria) within 8 weeks or occurrence of death. Follow up time for all DFS endpoints will be derived as follows:

Date of first occurrence of first deterioration event or censoring – date of randomization + 1.

In case there is no subsequent assessment within 8 weeks of first documented deterioration, the date of first documented deterioration will be considered as date of deterioration. For time-to-deterioration endpoints, death will be considered as event. If a subject had no post-baseline assessment and did not experience the event of interest, then DFS will be censored at the date of randomization and we will set DFS = 1 day, by convention. Also for the subjects with missing baseline, DFS will be censored at the date of randomization.

Continuous variables

Summary of continuous endpoints (e.g., change from baseline) will include the mean, standard deviation, median and range. In the context of change from baseline analyses, summary of baseline and post-baseline data will also be provided. Change from baseline analyses will be analyzed by an analysis of covariance (ANCOVA) model including stratification factors and baseline as covariates and 95% CI for treatment group difference will be provided.

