4.0 STUDY OVERVIEW AND STUDY PROCEDURES

4.1 Study Overview

This is a Phase 3 randomized double-blind, placebo controlled trial comparing the efficacy and safety of ABT-414 versus placebo, each as concurrent treatment with standard-of-care therapy of radiation therapy/TMZ plus adjuvant TMZ and followed by ABT-414/placebo monotherapy, in subjects with newly diagnosed GBM.

The study comprises a Screening Period of up to 7 weeks from surgery/biopsy; a 6-week concomitant Chemoradiation Phase; an Adjuvant Phase beginning approximately 4 weeks after completion of chemoradiation, and a Follow-Up Phase. The Adjuvant Phase is comprised of 28-day cycles, with subjects receiving concomitant TMZ and study drug (ABT-414/placebo) for the first 6 cycles, and study drug (ABT-414/placebo) monotherapy for the following 6 cycles. Subsequent cycles will start approximately 28 days from the start of the previous cycle, and the cycle schedule will not be affected by delays or interruptions in TMZ or ABT-414/placebo dosing. Adjuvant treatment will be discontinued once disease progression has been determined. A Final Study Drug Visit will be performed upon discontinuation of study drug (ABT-414/placebo) for any reason, followed by 35-Day and 49 Day Follow-Up Visit (± 3 days). If subjects are unable to attend the 49 Day Follow-Up Visit, a phone call should be performed to obtain adverse event and concomitant medication information. In the Follow-Up Phase, subjects who complete adjuvant treatment or discontinue study drug prior to disease progression will continue to undergo MR imaging and assessment of neurocognitive functioning and PRO approximately every 8 weeks up to and including at the time of disease progression, starting 8 weeks after the last scheduled PRO assessments in the Adjuvant Phase. After disease progression, overall survival will continue to be assessed quarterly.

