The start of the first cycle during the Adjuvant Therapy Phase will be scheduled approximately 28 days after the last day of radiotherapy. During the Adjuvant Therapy Phase, all subjects will receive oral TMZ 150 – 200 mg/m² once daily on Days 1 – 5 of each 28-day cycle for 6 cycles unless there is disease progression, unacceptable toxicity, or other reasons to discontinue. Subjects in Arm A will receive blinded ABT-414 1.25 mg/kg by intravenous infusion on Day 1 and Day 15 of each 28-day cycle for 12 cycles. Subjects in Arm B will receive blinded placebo IV infusion on Day 1 and Day 15 of each 28-day cycle for 12 cycles.

If after completing 12 cycles of adjuvant treatment, the subject is tolerating study drug (ABT-414 or placebo) and the Investigator believes the subject is continuing to benefit from ongoing study drug treatment, the Investigator may extend the Adjuvant Phase after consultation with the Neuro-Medical Oncology Chair or AbbVie Medical Monitor, as long as disease progression has not been determined.

Occurrence of disease progression to calculate PFS will be determined by the Investigator, based on local evaluation of images and other clinical information using the Response Assessment in Neuro-oncology (RANO) criteria ([Appendix I](#)). Post-baseline scans will be obtained \leq 14 days before Day 1 of each odd-numbered cycle (Cycles 1, 3, 5, etc.) of the Adjuvant Phase and \leq 14 days before each visit (approximately every 8 weeks) of the Follow-Up Phase. MR images will also be reviewed centrally by an independent blinded reviewer for radiographic evidence of disease progression. When study drug (ABT-414/placebo) is discontinued for any reason, a Final Study Drug Visit will be conducted. All subjects will have a 35-Day and 49-Day Follow-Up Visit (\pm 3 days) after the last dose of ABT-414/placebo. The 49-Day Follow-Up

Visit will focus on evaluation of ongoing adverse events. Overall survival will be assessed quarterly after study discontinuation.

Neurocognitive testing and patient-reported outcomes will be assessed approximately every 8 weeks during the Adjuvant and Follow-Up Phases, and then at disease progression.

Table 1. Study Activities – Chemoradiation Phase	Screening ^a		Chemoradiation Phase ^b						
	Screening 1	Screening 2	Day 1 Wk 1 (Fraction 1 of RT)	Day 1 of Wk 2	Day 1 of Wk 3	Day 1 of Wk 4	Day 1 of Wk 5	Day 1 of Wk 6	Day 1 of Wk 7
Informed Consent	X								
Medical and Oncologic History		X							

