- c. As per TMZ prescribing information, during the 28-day cycle of TMZ, a blood count for ANC and platelets should be performed 21 days (\pm 2 days) after the start of each TMZ cycle. If the ANC falls below 1,500/ μ L or if the platelet count falls below 100,000/ mm^3 , then blood counts should be performed weekly until recovery to these levels before TMZ dosing. A certified local lab may be used instead of central lab; if so, ANC and platelet results should be reported in the eCRF. Day 22 testing may be omitted for cycles in which TMZ is not administered or if local prescribing information allows for a different testing schedule for ANC and platelets.
- d. Final Study Drug Visit to be performed approximately 14 days after last dose of ABT-414/placebo. The physical examination and MR imaging from the first visit of the Follow-Up Phase will be used for the Final Study Drug Visit if these visits coincide (e.g., if the subject completes 12 cycles of Adjuvant Phase).
- e. To be performed 35 days (\pm 3 days) after the last dose of study drug (placebo or ABT-414). If the Final Study Drug Visit is more than 35 days after the last dose of study drug, then 35-day safety follow-up procedures will not be performed.
- f. Visits in Follow-Up Phase to occur every 8 weeks, beginning 8 weeks after Day 1 of the last odd-numbered cycle in the Adjuvant Phase.
- g. Height will be assessed at Screening only. Weight will be collected at all visits. Complete physical examination will be performed at Screening only. Symptom directed physical examination will be performed at all other designated visits as clinically indicated.
- h. Ophthalmology exam to be performed prior to ABT-414/placebo dosing on Day 1 (or up to 7 days prior to Day 1) of Cycle 1, Cycle 2, and every odd-numbered cycle thereafter (Cycles 3, 5, 7, etc.). Ophthalmology exam for Cycle 1 Day 1 may be omitted if the subject had no corneal microcysts or ocular adverse events during or after the Chemoradiation Phase. Ophthalmology exams may be discontinued if the subject has been on Level 1 eye drops with no ocular toxicity for 2 consecutive eye exams.
- i. Ophthalmology exam at Day 35 Follow-Up Visit to be done only if subject had corneal microcysts or other ocular findings related to ABT-414 or ocular steroids on previous exam and repeated at least every 8 weeks until satisfactory resolution of eye toxicities.

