4.2 Study Procedures

The study procedures outlined in [Table 1](#) and [Table 2](#) are discussed in detail in this section with the exception of the monitoring of treatment compliance (Section [5.10](#)) and the collection of adverse event information (Section [7.0](#)). All study data will be recorded on electronic case report forms (eCRFs), with the exception of pregnancy reporting forms and the neurocognitive function tests.

Procedures performed at Screening will serve as baseline, unless repeated prior to dosing; in which case the latter will serve as baseline. Unless otherwise noted, subsequent study procedures should be performed within 3 days prior to the scheduled study visit date when possible. Subjects who are not randomized will be considered a screen failure and will not be included in any intent-to-treat analyses.

Informed Consent

The informed consent for tissue and other pre-screening and for activities in the main study may be used separately or combined as a single informed consent document where allowed by local regulation and the IEC/IRB.

The IEC/IRB-approved informed consent must be signed and dated by each subject or the subject's legally acceptable representative prior to the submission of tumor tissue for screening, undergoing any study procedures or before any prohibited medications are withheld from the subject in order to participate in this study. Separate informed consent documents will also be required for the optional substudies in this protocol: for the collection of pharmacogenetic samples and the collection of tumor tissue post-treatment after disease progression, Section [15.3](#).

Tumor tissue testing will be conducted to confirm GBM diagnosis (central review of tumor histopathology), determination of *EGFR* amplification, *EGFRvIII* mutation and *MGMT* methylation status are all required for subject randomization. All clinical screening procedures should proceed simultaneously while tissue testing results are pending and should not be delayed until after EGFR amplification status is obtained.

For details on obtaining and documenting informed consents, Section [15.3](#).

Medical and Oncologic History

The following will be collected during the Screening Visit:

- Demographic information, including age, sex, and ethnicity. Ethnicity will include whether a subject is first generation Han Chinese.

- Complete medical history, including documentation of any clinically significant medical condition.

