A sensitivity analysis will be conducted to evaluate the robustness of the results, as exploratory and supportive of the primary PFS analysis. Accounting for subjects who died or progressed after more than one (> 1) missed visit, the following sensitivity analysis will be performed: Considering the date of the earliest missed radiological assessment following the last adequate radiological assessment prior to a subject's progression or death, as a date of progression.

No imputation will be used for subjects with no more than one missed visit in the sensitivity analysis. Details for the sensitivity analysis will be provided in the SAP.

Overall Survival for the MGMT Methylated, MGMT Unmethylated and EGFRvIII-Mutated Tumor Subgroups

OS analysis will be performed in the subgroup of patients with MGMT methylated MGMT unmethylated and EGFRvIII-mutation. The same methodology as for the primary OS analysis in the FAS will be applied.

Progression Free Survival for the EGFRvIII-Mutated Tumor Subgroup

PFS analysis will be performed in the subgroup of patients with EGFRvIII-mutation. The same methodology as for the PFS analysis in the FAS will be applied.

Time to Deterioration in Verbal Memory (HVLTR)

In the Phase 3 part of the study, time to deterioration in verbal memory, based on the HVLTR Total Recall, will be analyzed as a separate secondary endpoint. Other individual components and outcome from HVLTR and FAS verbal fluency will be analyzed on an exploratory basis.

The HVLTR Total Recall score will be computed by summing the total number of words recalled across 3 trials. Standardized scores (mean = 0, SD = 1) for each test are calculated using published normative data from a healthy population. At each assessment, change in the HVLTR total recall score relative to baseline will be calculated and verbal memory performance will be categorized as declined or not using the reliable change index (RCI) criterion based on the raw scores.

The deterioration is defined as satisfying the deterioration criteria without further improvement within 8 weeks or occurrence of death. TTD endpoints will be derived as follows:

TTD = Date of first occurrence of first deterioration event or censoring – date of randomization + 1.

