7.5.1 Definition of Visit Windows for HRQoL and Neurocognitive Function assessments

Visit windows for the HRQoL and Neurocognitive function assessments are displayed [Table 1](#).

Table 1. Visit window for HRQoL and Neurocognitive Function assessments

Scheduled Visit	Nominal Adjuvant Rx Day	Time Window
Baseline	Rx Day ≤ 1	Rx Day -21 to Rx Day 1
Adjuvant Phase Week 1	Adjuvant Rx Day 1	Rx Day 2 to Adjuvant Rx Day 29
Adjuvant Phase Week 9	Adjuvant Rx Day 57	Adjuvant Rx Day 30 to Adjuvant Rx Day 85 (i.e., Week 9 Day 1 \pm 4 weeks)
Adjuvant Phase Week 17	Adjuvant Rx Day 113	Day 86 to Day 141 (i.e., Week 17 Day 1 \pm 4 weeks)
	...	
Adjuvant Phase Week (8*X + 1)	Adjuvant Rx Day (56*X + 1)	Adjuvant Rx Day 56*X + 1 - 27 to Adjuvant Rx Day 56*X + 1 + 28 (i.e., Week (8*X + 1) Day 1 \pm 4 weeks)

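### The deterioration rule allows 8 weeks for a recovery to be seen, but assessments are themselves 8 weeks apart, so counted by dates a visit one day late cannot cancel a transient dip

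*SAP*

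**What the plan says.** **The rule.** SAP 10.1.1 defines a DFS event as meeting the deterioration criterion "without further improvement (i.e., failing to satisfy deterioration criteria) within 8 weeks or occurrence of death". It then adds: "In case there is no subsequent assessment within 8 weeks of first documented deterioration, the date of first documented deterioration will be considered" the date of deterioration. Protocol 14.6.2 has the same limit for verbal memory: "The deterioration is defined as satisfying the deterioration criteria without further improvement within 8 weeks or occurrence of death". It says MDASI-BT will be handled similarly. Neither document attaches a tolerance to the 8 weeks.

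**The schedule.** Protocol 4.1 states: "Neurocognitive testing and patient-reported outcomes will be assessed approximately every 8 weeks during the Adjuvant and Follow-Up Phases". The Protocol Table 2 notes carry the same step into follow-up: "Visits in Follow-Up Phase to occur every 8 weeks, beginning 8 weeks after Day 1 of the last odd-numbered cycle in the Adjuvant Phase". SAP 7.5.1 Table 1 sets nominal days at 56X + 1 (Adjuvant Rx Days 1, 57, 113 and so on). Its windows are contiguous; the Day 57 window, for example, is "Adjuvant Rx Day 30 to Adjuvant Rx Day 85".

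**Timing tolerances.** Protocol 4.2 says that, unless otherwise noted, "subsequent study procedures should be performed within 3 days prior to the scheduled study visit date when possible". Protocol 5.4 allows adjuvant study drug on Day 1 plus or minus 2 days.

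**The concern.** The confirmation step exists to remove transient dips, and it depends on the next visit falling inside the limit. Here the limit equals the visit spacing. If elapsed days are counted, a next visit held a day or more past day 56 cannot confirm or cancel anything, and the dip stands by default. Whether a recovery counts would then depend on scheduling and not on the patient.

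The endpoints at stake are DFS in MDASI-BT symptom severity, MDASI-BT symptom interference and HVLT-R total recall. These rank 5, 6 and 7 in the fixed sequence of SAP 5.6.2. Exploratory DFS in COWA-FAS uses the same rule. Two programmers working from the same data could also derive different events.

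**Working it through.** **1. Slack.** Limit: 8 × 7 = 56 days. Spacing: two 28-day cycles = 56 days, and Table 1 gives 57 − 1 = 113 − 57 = 56. Slack = 56 − 56 = 0 days.

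**2. Gaps the documents permit** (56 plus the second visit's offset minus the first's).
- Procedures 0 to 3 days early (Protocol 4.2): 53 to 59 days. Example: Day 54, then Day 113, gives 59.
- Day 1 ± 2 days (Protocol 5.4): 52 to 60 days. Example: Day 55, then Day 115, gives 60.

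So gaps of 57 to 60 days can occur with no departure from the schedule. On a date count, all of them miss the limit.

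**3. The windowed reading.** Under Table 1 a visit 3 days early stays in its own window, and the next windowed visit would always be available to confirm. A visit on Day 57 can be followed by an in-window visit as late as Day 141, which is 84 days later. The widest in-window gap is Day 30 to Day 141, or 111 days. The two readings can therefore disagree on the same data.

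**4. Illustration of size.** The dip rates and late shares are assumptions, not document figures.

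*Number of assessments.* Chemoradiation takes about 6 weeks and the break about 4, so assessments fall about 10, 18, 26 and 34 weeks after treatment start. Multiplying by 7/30.4375 gives 2.3, 4.1, 6.0 and 7.8 months. Protocol 1.0 reports median PFS of 6.3 and 8.0 months, so there are 3 or 4 scheduled visits plus one at progression: n = 4 or 5.

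*Late share L.* For independent visit offsets, L = (1 − P(equal offsets))/2.
- 90% of visits on the day, the rest spread evenly over 1 to 3 days early: P(equal) = 0.81 + 3 × (0.1/3)² = 0.8133, so L = 0.093.
- 75% on the day: P(equal) = 0.5625 + 3 × (0.25/3)² = 0.5833, so L = 0.208.
- L is not known. It is 0 if every visit is on its day, and 6/16 = 37.5% if 0, 1, 2 and 3 days early are equally likely.

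*False events in a stable patient.* Let each assessment be an independent dip with probability p, and let a dip at the last assessment count. Let A(m) be the probability of no event in the last m assessments. Then A(0) = 1, A(1) = 1 − p, and A(m) = (1 − p)A(m−1) + p(1 − L)(1 − p)A(m−2). The last gap ends in a progression assessment, which Table 2 asks for as soon as possible, so L = 0 is used at m = 2 and A(2) = 1 − p.

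For p = 0.10, false events = 1 − A(n):

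| L | n = 4 | n = 5 |
|---|---|---|
| 0 | 11.7% | 12.5% |
| 0.093 | 13.1% | 14.6% |
| 0.208 | 14.9% | 17.2% |

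Worked case, n = 5 and L = 0.208: A(3) = 0.9 × 0.9 + 0.07125 × 0.9 = 0.8741; A(4) = 0.9 × 0.8741 + 0.07125 × 0.9 = 0.8508; A(5) = 0.9 × 0.8508 + 0.07125 × 0.8741 = 0.8280. Here 0.07125 = 0.1 × 0.7917 × 0.9.

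The excess over L = 0 runs from 1.4 points (n = 4, L = 0.093) to 4.7 points (n = 5, L = 0.208).

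**The case against.** The strongest reply is that the SAP already has the answer. Section 7.5 windows each endpoint, Table 1 does so specifically for these instruments, and 5.3.2 classifies change at each time point. On an 8-week grid, 8 weeks may simply mean the next windowed visit. That reading is plausible and would remove the problem. But 10.1.1 is written in elapsed weeks and dates and never refers to Table 1, so the rule remains open to both readings.

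The early-visit allowance in Protocol 4.2 is also hedged, and Table 2 ties these assessments to the visit, before dosing. That weakens the Day 54 example. It does not restore slack, because the visit itself can move by 2 days under Protocol 5.4 and the interval is only approximate.

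The percentages are fairly criticised. Dip rates and late shares have no source in the documents. Of the 11.7% baseline, 10 points are dips at the last assessment, which the 8-week limit does not cause and which may be real at progression. Only the excess bears on this point.

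A reader might infer that the rule biases the arms, or that it changes a confirmatory conclusion. The documents support neither. The direction of any bias between arms is unknown: the trial is double-blind, and the cycle schedule is not moved by dosing delays. Protocol 1.0 reports a one-sided OS p-value of 0.628 at the interim, so the hierarchy did not reach ranks 5 to 7 there.

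**Conclusion.** The point holds as a defect in a stated rule combined with an ambiguity. A 56-day limit on a 56-day schedule has no slack, and permitted gaps of 57 to 60 days fall outside it when dates are counted. If the windowed reading was intended, it is not written down.

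The effect is confined to the three DFS secondary endpoints and COWA-FAS; OS and PFS are untouched. Under the stated assumptions the excess of false events is roughly 1 to 5 percentage points. That is an illustration, not an estimate for this trial, and it is zero under the windowed reading. What is at stake is the reported DFS estimates and whether they can be reproduced. Severity is minor to moderate.

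**What to change.** In both SAP 10.1.1 sentences and the Protocol 14.6.2 sentence, replace the 8-week limit by: *at the next assessment, scheduled or unscheduled, up to 12 weeks (84 days) after the first documented deterioration*. Keep the first deterioration as the event only when no assessment falls in that period.

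The 84 days are the 8-week interval plus 4 weeks (56 + 28). The SAP uses the same allowance in its 20-week PFS rule (2 × 8 + 4) and in the Table 1 windows. It covers every gap in step 2 and an on-time visit followed by the latest in-window visit. A cap in days is preferable to the next window alone, which could let a recovery 111 days later cancel an event. Table 1 windows also run from the first adjuvant dose and so do not serve subjects who never receive one. A wholly missed visit is still not bridged, since the following one is nominally at 112 days. In the illustration the late share becomes 0 and false events return to 11.7%-12.5%.

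The cost is three sentences and no new data. Slightly fewer DFS events would be counted, and a recovery first seen between 8 and 12 weeks could now cancel a deterioration.
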